4.3.2 Assessment of efficacy after treatment

The efficacy of the treatment will be determined 21 days post-treatment by collecting another two stool samples which will be microscopically examined for *T. trichiura* using duplicate Kato-Katz thick smears and potential co-infection with *S. stercoralis* applying the Baermann technique. Participants will be considered *T. trichiura* cured if no eggs have been found in the stool. EPG will be assessed by adding up the egg counts from the quadruplicate Kato-Katz thick smears and multiplying this number by a factor of six. Geometric and arithmetic mean egg counts will be calculated for the different treatment arms before and after treatment to assess the

corresponding ERRs. The stool samples collected 21 days post-treatment for efficacy assessment will further be re-tested with the same rapid diagnostic test and immunoassay used at baseline to determine fecal occult blood and calprotectin levels. Frequencies of subjects found positive with either of the two markers and by intensity category for calprotectin will be calculated by treatment arm.

At the end of the study (approximately 12 months post-treatment) all participants remaining positive for *T*. *trichiura* and other soil-transmitted helminths will be treated with albendazole-ivermectin, the currently best recommended treatment against *T*. *trichiura*.

Potential extended effects on follow-up helminth prevalences will be assessed using the same methodological approach as used for the efficacy assessment and will be based on stool samples collected 6 and 12 months post-treatment. Likewise fecal occult blood and calprotectin will be re-determined on the same stool samples.

To assess eventual reduction in morbidity indicators all trial participants will be asked to provide another fingerprick blood sample at the 6 and 12 month follow-up for Hb measurement. Anthropometric measurement including height, weight, MUAC and triceps skinfold thickness will be repeated on the same occasion. Children (6-16 years) will be asked to re-assess their own physical functioning in repeated questionnaire interviews during these two last follow-ups. Long-term satisfaction with the treatment will be asked 6 months past-treatment. Mean values for continuous outcomes and frequencies for binary/categorical outcomes will be calculated for each treatment arm and follow-up time point and compared using descriptive and repeated measurement analysis as detailed in section 7.3.

4.4 Measure to minimize bias

Study participants eligible for treatment will be randomly assigned to one of the two treatment arms using a computer-generated stratified block randomization code. The random allocation sequence with varying random blocks of four or eight and stratified by 2 levels of baseline infection intensity (light: <1000 EPG, and moderate plus heavy: \geq 1000 EPG *T. trichiura* infections) will be provided by a statistician. The treatment arms will have an equal number of participants with light infection intensity, although the number of light versus moderate/heavy infections are not expected to be equal in each arm, depending on the distribution of infection intensity in the recruited cohort. The study will be double blinded.

4.5 Study duration and duration of subject participation

The trial will last fourteen months. The screening for the baseline will start three weeks prior to the treatment. Follow-up screening will take place 14-21 days, 180 days and 360 days post-treatment and last each time for about three weeks. Schedules of visits are summarized below.

4.6 Schedule of visits

Page 67 of 176

	Screenin g	Baseline/Treatment/Safety			Follow up				
	-21 to -1 days	Hours			Days				
		0		3	24	21	180	185	360
Diagnosis (stool examination)	Х					Х	Х		Х
Gut morbidity (stool RDTs)	Х					Х	Х		Х
Informed consent	Х		tment						
Demographics	Х		treat					ent	
Medical history		Х	1 and					eatme	
Clinical examination		Х	zatio				Х	re-tro	Х
Pregnancy testing		Х	domi				Х	ctive	
Hemoglobin measurement		Х	Ran				Х	Sele	Х
W. bancrofti co-infection		Х					Х		Х
Physical functioning		Х					Х		Х
Capturing AEs				Х	Х	Х			
Capturing SAE				Х	Х	Х			
Treatment satisfaction				Х		Х	Х		

 Table 1. Schedule of visits of longitudinal study.

5. Selection of the trial subjects

5.1 Recruitment

The study will be carried out in community members aged 6–60 years in areas with moderate to high *T. trichiura* infection intensities (communities with a prevalence $\geq 25\%$) identified from earlier studies and/or based of experience of the local collaborating teams. The trial will be implemented as community-based study in order to recruit participants from a broad age range (6–60 years). Ideally, entire communities with a population size of < 1000 inhabitants will be included in the study for pre-screening and identification of *T. trichiura* cases to avoid potential selection bias of households. Another option might be to run the trial at schools and invite school-aged children and one adult for each child of the same household.

All adult community members, including parents/caregivers of minor participants, will be invited to participate in an information meeting to explain the purpose and procedures of the study, including potential benefits and risks. Parents/caregivers/potential participants will be encouraged to ask questions in an open discussion forum. During this session, they will be informed of preventive actions they can take to help protect their children from

acquiring *T. trichiura* and other STH infections in the future (e.g., adequate food preparation and defecation behavior).

Those parents/caregivers and their children who are interested in the study will be invited to complete the process of informed consent. See section 9.3 for details on obtaining informed consent. Only those participants who have written informed consent will be assessed for study eligibility criteria during screening procedures.

5.2 Inclusion criteria

- 1. Written informed consent signed by either the participant him/herself (≥18 years of age) or by parents and/or caregivers for children; and oral assent by child (aged 6–17 years).
- 2. Agree to comply with study procedures, including provision of two stool samples at the beginning (baseline) and on three follow-up assessments (approximately 3 weeks, 6 months, and 12 months later).
- 3. Aged ≥ 6 to ≤ 60 years.
- 4. At least two slides of the quadruple Kato-Katz thick smears positive for *T. trichiura* and infection intensities of at least 100 eggs per gram of stool (EPG).

5.3 Exclusion criteria

- 1. No written informed consent by individual/parents and/or caregiver.
- 2. Presence of major systemic illnesses, e.g., severe anaemia (below 80 g/l Hb according to WHO)[27], as assessed by a medical doctor, upon initial clinical assessment.
- 3. History of acute or severe chronic disease (e.g. cancer, diabetes, chronic heart, liver or renal disease).
- 4. Recent use of anthelmintic drug (within past 4 weeks).
- 5. Attending other clinical trials during the study.
- 6. Negative or low egg count (less than 100 EPG or less than 2 out of 4 slides positive) diagnostic result for *T. trichiura* eggs in the stool.
- 7. Pregnancy or lactating in the 1st week after birth (according to WHO guidelines within LF control programs [28]).
- 8. Known allergy to study medications (*i.e.* albendazole and ivermectin).

5.4 Criteria for discontinuation of trial

A subject can be discontinued from the study for the following reasons:

1. Withdraws from the study (this can happen anytime as participation is voluntary and there are no further obligations once a participant withdraws).

2. At the discretion of the Principal Investigator (PI) or co-PI, if the participant is not compliant to the requirements of the protocol.

Discontinued subjects will not be replaced. If, for any reason, a subject is discontinued from the study before the end of treatment evaluations, the safety procedures planned (adverse events monitoring) will be conducted.

5.5 Treatment of subjects

All *T. trichiura*-infected, consenting, and participating community members will be treated with the respective single or combination treatment regimen at day 0. 400 mg albendazole will be the product of Glaxo Smith Kline (Zentel®) and a single tablet administered. 3 mg tablets of ivermectin will be obtained from Merck (Stromectol®). The weight will be recorded for each participant and the correct dose evaluated and administered. Matching ivermectin placebo tablets will be produced by the University of Basel, Switzerland. To ensure double-

Page 69 of 176

blinding the tablets will be repacked into neutral separate plastic bags each containing one albendazole tablet and the maximum number of ivermectin tablets with regard to weight and dose or the corresponding number of placebo tablets. Since albendazole and ivermectin are known to be better absorbed in humans after a high-fat meal was consumed, participants will receive a local high-fat breakfast (sandwich with *e.g.* oily sardines) prior to treatment [29, 30].

All drugs will be administered in the presence of the investigator(s), and ingestion confirmed. This will be recorded with the time and date of closing. Subjects will be asked not to take any drugs other than those prescribed by the study medical team. After ingestion of the medication, the subjects will be observed for 3 hours to ensure retention of the drug. Vomiting within 1-hour post-dosing will require re-dosing. The subjects will not be allowed more than one repeated dose. No re-administration will be needed for subjects vomiting after one hour. The Principal Investigator is responsible for drug accountability at the study site. Maintaining drug accountability includes careful and systematic study drug storage, handling, dispensing and documentation of administration.

To avoid interference of potential on-going control programs against helminthiases with the infection status of the trial participants, communication with local stakeholders will be established to ascertain that trial participants will not undergo MDA treatment. Missed-out rounds of planned MDA against STH in the participating study communities be substituted with a free community-wide single-dose treatment (i.e., albendazole 400 mg + ivermectin 200 μ g/kg) against STH as well as *S. stercoralis* infection at the study endpoint (after the day 360 follow-up assessment) offered by the study team. At each follow-up time point, participants will be interviewed whether they had taken anthelmintic treatment (e.g. self-purchased, obtained from clinics etc). Participants found to be severely anemic at any of the three assessment time points (baseline, 6 and 12 months post-treatment) will be referred to the next hospital/clinic.

5.6 Concomitant therapy

All medications taken one month before and during the study period until the last stool examination must be recorded with indication, dose regimen, date and time of administration.

Medication(s)/treatment(s) permitted during the trial:

- Analgesics and antipyretics are allowed to be given to the subjects in case of fever, antiemetics to prevent nausea and vomiting and/or antibiotics to prevent or treat bacterial superinfection.

Medication(s)/treatment(s) NOT permitted during the trial:

- No other active drugs against helminths are permitted during the trial.

6. Safety assessments

Few AEs have been reported following ivermectin-albendazole co-administration in STH-infected individuals. The most common AEs were abdominal cramps, headache, fatigue, nausea, diarrhea, fever and vertigo [8, 9, 31]. The safety profile of co-administered ivermectin and albendazole will be assessed through the recording, reporting and analysis of baseline medical conditions, AEs and a physical and clinical examination.

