	 a) To evaluate the safety and tolerability of the two treatment regimens b) To evaluate the egg reduction rate (ERR) of the two treatment regimens against T. trichiura c) To determine the CRs and ERRs of the drugs in study participants (6-60 years) infected with hookworm, Ascaris lumbricoides and Strongyloides stercoralis d) To investigate potential extended effects on follow-up helminth prevalences (6 and 12 months post-treatment) of the two treatment regimens (as assessed among participants with cleared infection on days 21 and 180) e) To compare CRs based on egg counts retrieved from novel PCR-based and standard microscopic diagnosis f) To assess potential differences in susceptibility to the two treatment regimen between the hookworm species, Necator americanus, Ancylostoma duodenale and A. ceylanicum, as classified through the novel PCR-based diagnosis g) To characterize Trichuris strains from different epidemiological settings h) To evaluate potential benefits from deworming on morbidity indicators (e.g. anemia, occult fecal blood, calprotectin, growth standard safe aphysical functioning) 	
Study design	Double blind, randomized controlled trial	
Study product / intervention	Administration of a single oral dose of ivermectin + albendazole	
Comparator(s)	albendazole (400 mg) alone	
Key inclusion / Exclusion criteria	Inclusion: School-aged children or adults (6-60 years) infected with T. trichiura with at least two slides of the quadruple Kato-Katz thick smears positive and infection intensities of at least 100 eggs per gram of stool (EPG), able and willing to be examined by a study physician at the beginning of the study and to provide two stool samples at baseline and on the three follow-up assessments (approximately 3 weeks, 6 months, and 12 months later), absence of major systemic illnesses or history of chronic disease, written informed consent signed by parents and/or caregivers for minors; and oral assent by school-aged children, no known allergy to study medication, no recent	

	anthelminthic treatment (past 4 weeks) and for girls/women of fertile age: not being pregnant or lactating in the 1 st week after birth.				

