	Exclusion: No written informed consent, any abnormal medical conditions or history of acute or severe chronic disease, recent use of anthelminthic drug (past 4 weeks), negative diagnostic or low egg count (less than 100 EPG or less than 2 out of 4 slides positive) result for T. trichiura , pregnancy or lactating in the 1 st week after birth.				
Primary Endpoints	CR on T. trichiura				
Secondary Endpoints	 ERR against T. trichiura CRs and ERRs against A. lumbricoides, hookworm and S. stercoralis Safety Diagnostic performance Molecular characterization of Trichuris spp. Changes in morbidity 				
Exploratory Endpoints	None				
Interim Analyses	None				
Study Duration	14 months total; up to 12 months per participant				
Schedule	06/2018 of first-participant in (planned) 08/2019 of last-participant out (planned)				
Study centres	Multinational study with trial sites in Côte d'Ivoire, Lao PDR and Pemba Island (Tanzania)				
Measurements & procedures	Two stool samples will be collected if possible on two consecutive days or otherwise within a maximum of 5 days. The medical history of the participants will be assessed with a standardized questionnaire, in addition to a clinical examination carried out by the study physician before treatment. All participants will also be interviewed before treatment, 3 and 24 hours and 3 weeks after treatment about the occurrence of adverse events. Children (6-16 years) will additionally be asked to rate their own physical functioning by replying to a pre-tested questionnaire at baseline and 6 and 12 months after treatment. The efficacy of the treatment and potential extended effects on follow-up prevalence will be determined 14-21 days, 6 months and 12 months post-treatment by collecting another two stool samples. Subjective treatment satisfaction will be assessed 3 hours, 3 weeks and 6 months after treatment to				

	investigate relationship with treatment compliance and observed efficacy in reducing egg output and morbidity.

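### The Pemba protocol does not exclude people already taking drugs that interact with the study medication, and has no explicit in-trial ban on them, although the other texts have both rules

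*Combined protocol and SAP*

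**What the plan says.** Section 5.6 of the Pemba protocol contains one prohibition: "No other active drugs against helminths are permitted during the trial". Section 5.3 lists eight exclusion criteria, the last being "Known allergy to study medications"; none concerns interacting medication. The Pemba synopsis has no such item either.

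Some Pemba wording gives partial cover:
- The synopsis requires "absence of major systemic illnesses or history of chronic disease" and excludes "any abnormal medical conditions or history of acute or severe chronic disease".
- Section 5.2 requires that participants "Agree to comply with study procedures".
- Section 5.4 allows discontinuation "if the participant is not compliant to the requirements of the protocol".
- Section 5.5 adds: "Subjects will be asked not to take any drugs other than those prescribed by the study medical team".
- Section 5.6 also provides for recording: "All medications taken one month before and during the study period until the last stool examination must be recorded", with indication, dose and date.

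The Swiss protocol excludes current users of interacting drugs in its synopsis and in 5.3 (criterion 9), giving cimetidine, praziquantel and dexamethasone as examples for albendazole and warfarin for ivermectin. Its 5.6 bans such drugs during the trial. Laos has the same rules (synopsis, 5.3 criterion 10, 5.6), and so does the Côte d'Ivoire text as printed (synopsis, 5.3 criterion 9, 5.6).

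The SAP introduction takes the Pemba version of 13 February 2018 as current. Its deviations section counts as major both entry without meeting the entry criteria and receipt of an excluded concomitant therapy. It gives no drug list for the second. Major deviations remove a participant from the per-protocol and safety populations.

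**The concern.** The three trials are meant to share one design and one drug regimen, yet the rule on who may be dosed differs. Someone taking cimetidine at screening is ineligible in Laos, while nothing in Pemba 5.3 or 5.6 names that drug. The supplement overview lists how Pemba differs from the Swiss text and does not declare this difference; the table of protocol changes does not mention it either.

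Two things are at stake. One is safety practice: a participant may be dosed in Pemba for whom the sponsor's other texts say not to dose. The other is analysis: the same exposure can change population membership in one country and not in another, while the SAP tabulates the countries side by side and adds a total column for efficacy.

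**Working it through.** The point rests on comparing texts. The plan states no figure to reproduce.

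**Where the rule appears**

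| Text | Synopsis | 5.3 exclusion | 5.6 ban |
|---|---|---|---|
| Swiss (12.06.2018) | yes | yes, item 9 | yes |
| Laos | yes | yes, item 10 | yes |
| Côte d'Ivoire, as printed | yes | yes, item 9 | yes |
| Pemba (13.02.2018) | no | no (eight items) | no |

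The printed Côte d'Ivoire text is supporting evidence only. Its synopsis is marked v1.01 of 12.06.2018, whereas the SAP names v1.03 of 22.11.2018.

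**What other Pemba rules reach, drug by drug**

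- Praziquantel: covered. Pemba 5.3 item 4 excludes anthelmintic use in the past 4 weeks, and 5.6 bans other anthelmintics during the trial.
- Warfarin and dexamethasone: not named. Users are caught only if the underlying illness excludes them, under 5.3 items 2 and 3 or the broader synopsis wording.
- Cimetidine: not named. Nothing in 5.3 or 5.6 reaches the drug itself. The synopsis phrase on abnormal medical conditions might catch some users through the condition being treated.

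**Entry or in-trial?** The request in 5.5 is broader than an interaction ban and applies to cimetidine once a person is under study. It does not make someone already on the drug ineligible. So the gap is mainly at entry.

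**Consequence in the SAP populations**

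1. Laos, on cimetidine at entry: exclusion criterion 10 is broken. That is a major deviation, so the participant leaves the per-protocol and safety populations.
2. Pemba, same exposure: no Pemba criterion is broken. If an excluded therapy means one excluded by that country's protocol, which is the natural reading, the participant stays in both populations. The SAP does not state this reading.
3. Available-case population: defined by randomisation, a positive baseline and at least one non-missing endpoint. Concomitant drugs play no part, so the main efficacy result changes by 0.
4. Within Pemba: both randomised arms are under the same rule, so the comparison is not biased.

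**How many people?** The documents give no rate of use. Purely as an assumption, take 0.5% to 2%:

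- Pemba 7.2 plans 600: 600 × 0.005 = 3 and 600 × 0.02 = 12.
- The SAP's 143 per arm gives 2 × 143 = 286: 286 × 0.005 = 1.4 and 286 × 0.02 = 5.7.

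**What a listing could show.** With no events among m users, the one-sided 95% upper limit for the event rate is 1 − 0.05^(1/m). For m = 3, 6 and 12 this is 63%, 39% and 22%. A listing of that size is descriptive only.

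**The case against.** The best reply is that Pemba needs no separate rule. Participants are asked to take no drugs beyond those the study team prescribes, must agree to comply, can be discontinued if they do not, and see a physician who takes a medical history before treatment. During the trial this covers most of what an interaction ban would cover, and that part of the reply stands. It does not settle entry: the Swiss and Laos texts carry the same request in their own 5.5 and still add both the exclusion and the ban.

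A reader might infer that the rule was removed for Pemba. The dates do not support that. The Pemba text is dated 13.02.2018 and was accepted on 23.05.2018, before the Swiss version of 12.06.2018. It is the earlier text and was not harmonised later.

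A reader might also conclude that cimetidine is the main drug left uncovered. It is the one with the least indirect cover, but the documents do not allow a ranking of how many users of cimetidine, dexamethasone or warfarin would pass screening.

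Finally, no harm is shown. That is correct: the documents name interactions as grounds for exclusion but do not quantify any effect on safety or efficacy.

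**Conclusion.** The concern holds as an inconsistency in who may be dosed, mainly at entry, for users of cimetidine, dexamethasone or warfarin without an otherwise excluding illness. It is a low-priority improvement. The number affected is unknown; 3 to 12 of 600 rests wholly on the assumed 0.5% to 2%.

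Two stronger readings should be resisted. The documents do not support a claim that Pemba efficacy results are biased, because neither the available-case set nor the randomised comparison depends on this rule. Nor do they support a claim that Pemba participants were harmed or could take any drug freely.

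The omission itself is certain from the text. The difference in per-protocol and safety membership is certain on the Laos side, for use at entry. On the Pemba side it assumes that the SAP's deviation item follows each country's own protocol.

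**What to change.** If Pemba enrolment is open, copy the Swiss exclusion criterion (5.3 item 9) into Pemba 5.3 and the synopsis, and the Swiss ban into Pemba 5.6. The cost is three lines, an amendment needing ethics approval, and a few participants becoming ineligible.

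Enrolment is probably over: the last participant was planned to finish in 08/2019 and the SAP is dated 14.9.2020. In that case:

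- Leave the per-protocol sets as defined. Pemba users of the three drugs who are otherwise eligible met every Pemba criterion. Praziquantel users are already barred by Pemba's anthelmintic rules and need no new handling. A re-run that adds users back across countries would return to the Laos set people whom the SAP excludes.
- State in the SAP that an excluded concomitant therapy is the one excluded by each country's protocol.
- List the Pemba participants dosed while taking cimetidine, dexamethasone or warfarin, with their adverse events, as description only.

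This costs one sentence and one listing. No new data collection is needed, since Pemba 5.6 requires medication to be recorded. However, the data-entry text in Pemba 10.2 does not name concomitant medication, so the entries may have to be retrieved from the CRFs. This route cannot undo dosing already given.
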